11.5 Endpoints Analyses

11.5.1 Primary Efficacy Endpoint Analyses

The primary efficacy endpoint is the change from baseline to 8 weeks post treatment initiation in HDRS-17 score.

The change in HDRS-17 from baseline to 8 weeks post treatment initiation will be compared between the treatment groups using a repeated measures analysis of covariance (ANCOVA, SAS® MIXED procedure). The model will include the following fixed effects: treatment group, visit, treatment group by visit interaction

with Baseline HDRS-17, and center entered as covariates. If covariates are identified in the prognostic factor analysis, they may be added to the model as well. Baseline HDRS-17 scores will be entered as a continuous variable so that the potential for co-linearity problems will be minimized. The treatment group by center interaction will be evaluated as well, but not as part of the principal statistical evaluation.

The unstructured covariance matrix structure will be used. If the model does not converge, then either the compound symmetry or autoregressive (whichever model has the lower AIC statistic) covariance matrix structure will be used instead. At this time point (up to 8 weeks) we do not expect a high proportion of dropouts, as a placebo effect of the sham treatment is expected and was taken into consideration in the design of the study. Thus, any missing data at 8 weeks post treatment initiation can be considered missing at random. Therefore, since repeated measures ANOVA is also an imputation method, for this evaluation no other method of imputation of missing data is considered beyond the model estimates. Nevertheless, should the missing at random assumption prove to be incorrect, a sensitivity analysis using other methods for data imputation mentioned in Section 7 may be performed.

Mock SAS code for the analysis:

```
Proc Mixed data=HDRS17;
  class visit group center subjectid;
  model change_HDRS17 = baseline_HDRS17 visit group visit*group;
  repeated / type=un subject=subjectid;
  lsmeans group*visit / pdiff cl;
  random center;
run;
```

The principal statistical analysis will be a comparison between the treatment groups, derived from the visit by treatment group interaction term from the model. The adjusted mean change from baseline in HDRS-17 scores at 8 weeks post treatment initiation will be estimated from the model (LS Means) interaction term for each group, as well as the difference between the adjusted means, and will be presented together with 95% confidence intervals. The null hypothesis will be rejected in favor of the alternative hypothesis and the study deemed

successful if the p-value is <0.05 and the mean change HDRS-17 in the active group is higher than that of the sham group.

The primary analysis model uses likelihood-based inference that is valid under a missing at random assumption.

Cohen's D will be calculated and presented as well as a measure of the clinical effect size of the change from baseline HDRS-17 at week 8. An effect size can also be calculated using methods described in "Effect sizes for growth-modeling analysis for controlled clinical trial in the same metric as for classical analysis", *Psychol Methods*. 2009 March; 14(1): 43-53), where $ES = \text{difference between LSmeans} / \text{Pooled SD of baseline HDRS-17 score}$.

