(visit 3) and at  $8\pm 1$  weeks post visit 2 (visit 4). During visits 3 and 4 subject's depression symptoms will be assessed by the site team qualified raters using the study questionnaires and the subject self-reported questionnaire. Study visit 4 will be the end of the double-blind phase and the beginning of the open label extension period. At this visit, subject's compliance with the treatment regimen during the DB phase will be assessed. Subjects who would not fulfill the minimum stimulation requirements during the DB phase (non-compliant subjects) will complete their participation in the study. DB phase treatment regimen compliant subjects will be offered to participate in a  $8\pm 1$  weeks open-label period with an active device. Subjects who choose to continue to the open label phase will be trained as per their recommended treatment regimen (see Figure 5) by the study central trainer in an on-site or remote fashion. (regardless their prior DB treatment assignment) and will follow this treatment regimen for the next 4-8±1 weeks. Subjects will return for follow up visits (on-site or remote) at  $4\pm 1$  weeks post visit 4 (visit 5) and at  $8\pm 1$  weeks post visit 4 (visit 6). During visits 5 and 6 subject's depression symptoms will be assessed by study team qualified raters and the PRO (electronic or hard copy) using the study questionnaires. At study visit 5 the subjects response to treatment, according to HDRS, will be re-evaluated and treatment regimen may be amended accordingly (see Figure 5), re-training will be performed by the central trainer, if required. Study visit 6 will be the end of study visit during which the device will be returned, final data will be collected, and the subjects will be exited from the study.

Subjects found ineligible by the procedures required at screening will be marked as 'screen failure' on the screening & enrollment log and will not take part in the study. Screen failure subjects will not be included in the intention-to-treat analysis, nor will they be counted as part of the target subject sample number.

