## 12.4. Sample Size Estimation

Sample size estimation is driven by the hypothesis testing of the primary endpoint and will be calculated using the sample size equation for a two-sample t-test, even though for the final analysis we may employ a statistically more powerful model such as repeated measures ANOVA.

An effect size of 0.5 (Cohen's d- Cohen, J. (1988). Statistical power analysis for the behavioral sciences (2nd ed.) Hillsdale, NJ: Lawrence Earlbaum Associates.) is considered a moderate effect size, and is lower than effect sizes seen for similar studies, thus 0.55 will be considered in this study for sample size estimation as the minimally important clinical effect size to be detected.

In a company feasibility study of the Relivion®DP device we evaluated the mean change from baseline up to weeks 3 and 6 in HDRS-17 score. The 3 week results were a (baseline adjusted) mean change of -5.95 points (95% CI:[-8.1,-3.8]) and the standard deviation of 4.2 points. The 6 week results were a (baseline adjusted) mean change of -8.4 points (95% CI:[-10.6,-6.26]) and the standard deviation of 5.6 points. This study had no control arm thus considering a minimally important effect size (Cohen's D) of 0.5 (and assuming equal group variances rounded up to 5 and 6 at 3 and 6 weeks respectively) we would expect an HDRS17 score reduction in the sham group of about 3.45 points at 3 weeks and 5.4 points at 6 weeks unless the treatment arm has a greater reduction.

In planning their study, Levkovitz et al (Brainsway Ltd.) assumed that effect size of 0.5 and a difference of 3.75 points between active to sham subjects treated with TMS will provide a significant clinical effect. The final results show a significant reduction in HDRS21 of 6.39 points in the TMS group compared to 3.28 in the sham group with an effect size of 0.76. Neuronetics Inc. reported an HDRS17 score reduction of 5.2 points in the active TMS group compared with a 3.3 point reduction in the sham group (ES>0.5), with a

 Neurolief Brain Innovation	MOOD: CLINICAL INVESTIGATION PLAN	Doc No.: CL-CIP-201 Rev: REV.3 / 09June2021 Pg. 71 of 92
--	--	--

minimal considered effect size of 0.4. Moreover, in a large analysis of the FDA database of antidepressant medications, Khan et al reported that the mean percentage reduction from the baseline in HDRS17 score was 40.7% for active treatment and 30.9% for placebo.

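### If the unstructured fit fails, the fallback for the primary model allows only one structure with two visits, and it forces equal variance at weeks 4 and 8; an unlikely event, but cheap to repair

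*SAP*

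**What the plan says.** SAP 11.5.1, repeating Protocol 12.9.1, sets the covariance in two steps. First: "The unstructured covariance matrix structure will be used". Second, only on non-convergence: "then either the compound symmetry or autoregressive (whichever model has the lower AIC statistic) covariance matrix structure will be used instead".

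Three other statements fix the shape of the model.

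- The mock code has change as the response and baseline as a covariate ("model change_HDRS17 = baseline_HDRS17 visit group visit*group"), so baseline is not a repeated row.
- The double-blind phase has two post-baseline HDRS ratings (Protocol 8.2: "During visits 3 and 4 subject's depression symptoms will be assessed by the site team qualified raters"; Protocol Table 1 agrees). The open-label visits have their own analyses in SAP 11.5.7.
- The success test is the week-8 group contrast, "derived from the visit by treatment group interaction term from the model", judged at p<0.05 with a 95% confidence interval.

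Neither document names a heterogeneous-variance fallback or empirical (sandwich) standard errors. SAP 11.5.4 and 11.5.5 apply a similar model to MADRS, CGI-S, CGI-I, QIDS-SR-16, HDRS-21 and the HDRS-17 total score.

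**The concern.** A fallback should keep the success test valid when the preferred fit fails. This one appears to offer a data-driven choice between two structures, but with two visits there is only one. That structure estimates a single variance from the week-4 and week-8 residuals together and uses it for the week-8 contrast. In change-from-baseline data the variance often grows with time, and the SDs in Protocol 12.4 point that way. If the week-8 variance is the larger, the pooled figure understates it. The p-value and confidence interval that decide the trial would then be too favourable, and no other part of the plan corrects them.

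**Working it through.** **Inputs**

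- Two post-baseline visits per subject (Protocol 8.2 and Table 1; SAP 11.5.1).
- Feasibility SDs of change in Protocol 12.4: 4.2 at week 3 ("mean change of -5.95 points (95% CI:[-8.1,-3.8]) and the standard deviation of 4.2 points") and 5.6 at week 6. The protocol then works with "assuming equal group variances rounded up to 5 and 6 at 3 and 6 weeks respectively".
- 53 per group, 3.3-point difference, SD 6, two-sided 5% (Protocol 12.4).
- Assumptions: the week-3 and week-6 SDs stand in for weeks 4 and 8; autoregressive means homogeneous AR(1).

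**The plan's own figure.** A two-sample t-test with difference 3.3 and SD 6 has power 79.3% at 52 per group and 80.1% at 53. The stated 53 per group is reproduced, and this point does not affect it.

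**Step 1: the two structures coincide.** With two visits, compound symmetry and AR(1) both give s² × [[1, r], [r, 1]]. REML fits to three simulated two-visit data sets (SDs 5 and 6, 10% missing at week 8) gave identical likelihood, AIC (861.888 for both in the first), covariance matrix and week-8 standard error. Unstructured has three parameters: two variances and a covariance.

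**Step 2: effect on the week-8 standard error.** With complete data and n per arm:

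- separate variances: SE = s8 × √(2/n)
- fallback: SE = √((s4² + s8²)/2) × √(2/n)
- ratio R = √((s4² + s8²)/2) / s8
- actual size of the nominal 5% test ≈ 2 × (1 − Φ(1.96 × R))

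For SDs 5 and 6: √((25 + 36)/2) = 5.52 and R = 5.52/6 = 0.920. For SDs 4.2 and 5.6: √((17.64 + 31.36)/2) = 4.95 and R = 4.95/5.6 = 0.884. At n = 53:

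| SD week 4 / week 8 | Ratio R | SE, separate variances | SE, fallback | 95% half-width, separate / fallback | Actual size |
|---|---|---|---|---|---|
| 5 / 6 | 0.920 | 1.166 | 1.073 | 2.28 / 2.10 | 7.1% |
| 4.2 / 5.6 | 0.884 | 1.088 | 0.962 | 2.13 / 1.88 | 8.3% |
| 5.5 / 6 | 0.959 | 1.166 | 1.118 | 2.28 / 2.19 | 6.0% |
| 6 / 6 | 1.000 | 1.166 | 1.166 | 2.28 / 2.28 | 5.0% |
| 6 / 5 (falling) | 1.105 | 0.971 | 1.073 | 1.90 / 2.10 | 3.0% |

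The last three rows are illustrations, not figures from the plan.

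**Step 3: simulation.**

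- In 20,000 null trials per setting (53 per arm, complete data, correlation 0.5 or 0.7), pooled variance rejected 7.1–7.2% (SDs 5/6) and 8.3% (4.2/5.6). Visit-specific variance rejected 5.0–5.1%.
- Full REML fits in 1,500 null trials (SDs 5/6, correlation 0.5; Monte Carlo error about 0.6 points) rejected 6.7% under compound symmetry against 5.1% under unstructured with complete data, and 6.2% against 4.1% with 10% missing at week 8.

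**Step 4: how firm are the SDs?** Protocol 12.4 prints confidence intervals beside them: [−8.1, −3.8] and [−10.6, −6.26], with half-widths 2.15 and 2.17. Protocol 7.6.2 gives n = 23, so the t quantile is 2.074. The implied SDs are 2.15 × √23 / 2.074 = 4.97 and 2.17 × √23 / 2.074 = 5.02, almost equal. The printed means are baseline-adjusted, so the intervals may come from a pooled-variance model. A paired test of 4.2 against 5.6 at n = 23 gives p of about 0.14 at correlation 0.5, 0.11 at 0.6 and 0.04 at 0.8.

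**Step 5: weight of the trigger.** If unstructured failed in 1% of such trials (an assumed figure), the overall size would rise by 0.01 × (7.1 − 5.0) = 0.02 to 0.01 × (8.3 − 5.0) = 0.03 percentage points. At 5% the rise would be about 0.1 to 0.17 points.

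**The case against.** The strongest reply is that the rule will almost certainly stay dormant. Unstructured is the planned matrix, and three covariance parameters in about 106 evaluable subjects should converge. This stands and sets the weight of the point. A reader might infer that the primary test as planned runs at 7% to 8%. The documents do not support that: those figures are conditional on a failed fit and on unequal variances.

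The evidence for unequal variances is also thin. The SDs come from weeks 3 and 6 of an uncontrolled 23-patient study, and the intervals printed beside them imply nearly equal SDs. This stands too, so rising variance is a plausible case and not an established one.

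The AIC tie does no harm in itself, since either label gives the same estimate, standard error and p-value. Nor would the change of structure pass unnoticed: it follows a visible convergence failure, and the structure used is a named choice. What the output would not show is whether the equal-variance assumption is sound.

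Autoregressive could mean the heterogeneous ARH(1), which with two visits equals unstructured. The SAP does not say so; homogeneous AR(1) is the ordinary reading.

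Of the other endpoints, the clinician-rated ones also have two double-blind post-baseline visits, so failure is just as unlikely there. QIDS-SR-16 is completed weekly (Protocol 9.1.3). If the weekly scores are modelled, failure is more plausible. Compound symmetry and AR(1) then differ and AIC does choose, but both still impose equal variance.

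**Conclusion.** The concern holds as a low-probability defect in a stated rule. With two visits the fallback is one model, and its week-8 standard error is wrong whenever the week-4 and week-8 variances differ; that follows from algebra and needs no assumed SD. The size does need an assumption. If the feasibility SDs carry over to weeks 4 and 8, the standard error is 8% (SDs 5/6) to 12% (4.2/5.6) too small and the 5% test runs at about 7% to 8%. The error is nil with equal SDs and reverses if the SD falls. All of this is conditional on the unstructured fit failing and on reading autoregressive as homogeneous AR(1). The planned analysis and the sample size are unaffected. The point deserves a change because the rule governs the success test of a pivotal study and the repair is small.

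**What to change.** Replace the fallback in SAP 11.5.1, and through it the similar models in 11.5.4 and 11.5.5, with this sequence on non-convergence:

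1. Refit with new starting values and a heterogeneous-variance structure (CSH or ARH(1)). With two visits these are the unstructured matrix in another parametrisation, so this step keeps visit-specific variances but may fail for the same reason; step 2 is therefore needed.
2. If that also fails, use compound symmetry with empirical (sandwich) standard errors, and report a week-8 ANCOVA adjusted for baseline and center as a supporting analysis.

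State also which QIDS-SR-16 records enter its model, visit scores or weekly scores, since that decides how likely the fallback is to be used there.

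The cost is a few lines of SAP text. Sandwich standard errors are slightly less stable in small samples. The week-8 ANCOVA drops subjects who have only Visit 3, which fits less well with the plan's missing-at-random reasoning; hence its supporting role.

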## 12.5. Interim Analysis

Planning one interim analysis that permits an increase in the sample size as described below does not additionally inflate the type I error [38]–[41]. In addition, the final analysis is performed using the conventional test as appropriate for the statistical hypothesis.

An interim analysis will be performed by an independent statistician once about 80% of the required number of subjects aged 22-70 have been randomized and completed the 8-week post treatment initiation visit. Depending on the outcome of the interim analysis, the study will either continue to the originally planned sample size, stop for futility, stop for efficacy, or continue with an increased sample size. These decisions will be made based on the conditional power (CP), which is defined as the conditional probability that the result will exceed a critical value at the interim given the observed effect size.

Note that the interim analysis will be conducted on the ITT, mITT, PP and mYITT analysis sets, and the study will be stopped due to futility only if the interim effects in all populations fall below the CP threshold.

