### 12.5.1. Procedure

After all the relevant data will be entered into the database, and the database cleaned, a soft lock to the database will be performed. An independent un-blinded statistician (not the study statistician) will perform the assessments described below. A designated data monitoring team will recommend whether to stop the study once the interim results are available.

 Neurolief Brain Innovation	MOOD: CLINICAL INVESTIGATION PLAN	Doc No.: CL-CIP-201 Rev: REV.3 / 09June2021 Pg. 72 of 92
--	--	--

At the interim analysis, the data of the evaluable subjects in the ITT, mITT, PP and mYITT sets will be analyzed.

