- If the result is “overwhelming” i.e. primary endpoint at the interim analysis is statistically significant at a 0.04108 level of significance, then stop the study for success. This was calculated based on an adaptive design with one interim analysis planned to either stop the study for futility or early success at the interim with a Lan-DeMets alpha spending approach using a Pocock type function, where at the interim the study will be stopped for success if the null hypothesis is rejected at an alpha level of 0.04108.

Note that the interim analysis will be conducted on all populations (ITT, mITT, PP and mYITT analysis sets, see **Section 12.7**), and the study will be stopped due to futility only if the interim effects in all populations fall below the threshold.

The un-blinded statistician will also calculate the sample size required to test the null hypothesis to achieve 80% power at 4.108% level of significance given the current trend.

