#### **12.5.4. Controlling the Alpha Level for the Primary Endpoint**

The overall alpha level for this study is 5%. According to [Müller 2001; Jonathan 2001 Broberg 2013 and Siu 2001], planning an interim analysis that permits an increase in the sample size as described above does not inflate the type I error.

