--	--	--

The null hypothesis will be rejected in favor of the alternative hypothesis and the study deemed successful if the p-value is <0.05 and the mean change HDRS17 in the active group is higher than that of the sham group.

Cohen's D will be calculated and presented as well as a measure of the clinical effect size of the change from baseline HDRS17 at week 8. An effect size can also be calculated using methods described in "Effect sizes for growth-modeling analysis for controlled clinical trial in the same metric as for classical analysis", *Psychol Methods*. 2009 March; 14(1): 43-53), where ES = difference between LSmeans / Pooled SD of baseline HDRS17 score.

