## **14. Study Administration**

### **14.1. Data monitoring committee**

An independent data monitoring committee (DMC) will be responsible for safeguarding the interests of trial participants by assessing the safety and efficacy of the interventions during the trial. The DMC will

provide recommendations to sponsor about stopping or continuing the trial or making modifications to enhance safety of trial participants and/or the value of the information collected, or to protect the integrity of the study.

The data reviewed by the DMC will include a summary of the following topics:

- Safety monitoring: data related to the safety of the subjects, including any adverse events or side effects related to the treatment
- Efficacy monitoring: interim efficacy analysis and recommendations

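### Interim efficacy stop at two-sided 0.04108 with the final test left at 0.05: overall type I error is about 6.5%, not 5% (86 of 106 evaluable, futility non-binding, no sample size increase)

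*SAP*

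**What the plan says.** **Interim look.** Protocol 12.5.3 plans one look at 86 evaluable subjects, about 80% of 106. It derives the efficacy level from Lan-DeMets spending with a Pocock-type function: "at the interim the study will be stopped for success if the null hypothesis is rejected at an alpha level of 0.04108". The same section has a futility rule (conditional power below 29.14%), a sample size increase up to 250, and a Favorable zone (conditional power of at least 80%) in which the trial continues to 106.

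**Final look.** Protocol 12.9.1 has "the study deemed successful if the p-value is <0.05", and SAP 11.5.1 repeats it: "successful if the p-value is <0.05 and the mean change HDRS-17 in the active group is higher than that of the sham group". SAP 9.2 opens the secondary endpoints at a primary p of .05 or less. Protocol 12.5 adds that "the final analysis is performed using the conventional test as appropriate for the statistical hypothesis".

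**Alpha control.** Protocol 12.5.4 and SAP 9.1 state 5% overall. SAP 9.1 lists the early efficacy test as an exception to the 5% level but takes nothing off the final test. The justification in protocol 12.5.4 is that "planning an interim analysis that permits an increase in the sample size as described above does not inflate the type I error".

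**Futility in practice.** Protocol 12.5.3 says "the study will be stopped due to futility only if the interim effects in all populations fall below the threshold", across four analysis sets. Under protocol 12.5.1, "A designated data monitoring team will recommend whether to stop the study once the interim results are available". Under protocol 14.1 the DMC will "provide recommendations to sponsor about stopping or continuing the trial".

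**What happened.** SAP 2.2.1 reports a Favorable interim result and continuation to 124 without an increase.

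**The concern.** The plan gives the trial two chances to succeed. It spends 0.04108 of the 0.05 at the first and then tests at the full 0.05 at the second. Naming an alpha-spending function implies a reduced final level, and none is given. The argument in protocol 12.5 and 12.5.4 concerns raising the sample size. It does not cover an added opportunity to stop for success.

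This is a pivotal study for marketing applications that claims 5% overall. At 106 subjects, a final p between about 0.028 and 0.05 would be declared a success without alpha control, and would then open secondary and tertiary testing under SAP 9.2.

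That the interim is past and the trial continued does not restore the level. Type I error belongs to the whole rule, and not crossing at the interim does not return the alpha.

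**Working it through.** **Inputs.** Interim level 0.04108, 86 evaluable and 106 final (protocol 12.5.3); final level 0.05 (protocol 12.9.1, SAP 11.5.1); difference 3.3, SD 6, so d = 3.3/6 = 0.55 (protocol 12.4); 1:1 allocation.

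**The plan's own figures.** A two-sample t-test with 53 per arm at d = 0.55 has 80.1% power at two-sided 5%, so the fixed-sample calculation reproduces. The interim level does not. Pocock-type spending is 0.05 × ln(1 + (e − 1)t), which gives 0.0432 at t = 0.80 and 0.0436 at t = 86/106 = 0.811. The value 0.04108 corresponds to t of about 0.742.

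**Type I error.** Under the null, (Z1, Z2) is bivariate normal with correlation √(86/106) = 0.901. Critical values are 2.0427 (interim) and 1.960 (final).

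- Overall = P(|Z1| > 2.0427) + P(|Z1| ≤ 2.0427 and |Z2| > 1.960) = 0.0411 + 0.0235 = **0.0646**.
- Benefit direction only: **0.0323**, against 0.025.
- Simulated two-sample t-tests (43 per arm at interim, 53 at final, 2,000,000 null trials): 0.0649 and 0.0325.

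**By number analysed at the end** (futility non-binding, no increase):

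| Final n | Two-sided error, final 0.05 | Final level restoring 5% if 0.04108 stands |
|---|---|---|
| 100 | 6.2% | 0.0314 |
| 106 | 6.5% | 0.0279 |
| 112 | 6.7% | 0.0253 |
| 124 | 7.0% | 0.0219 |

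With final level 0.0279 at 106, the t-test simulation gives 0.0502 two-sided and 0.0251 in the benefit direction. If the interim level is instead re-derived as 0.0436 at 86/106, the final level is about 0.024.

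**Other readings of the rules.** Take conditional power at the observed trend to 106: CP = Φ[(z1/√t − 1.960)/√(1 − t)]. Then CP < 29.14% means z1 < 1.550. Benefit-direction error is:

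| Rule order and final size | Futility non-binding | Futility binding |
|---|---|---|
| Efficacy rule first, no increase | 3.23% | 2.87% |
| Efficacy rule first, recalculated n up to 250 | 3.07% | 2.71% |
| Efficacy rule first, straight to 250 | 2.92% | 2.56% |
| Favorable overrides the efficacy stop, no increase | 2.64% | 2.29% |
| Favorable overrides, recalculated n up to 250 | 2.48% | 2.12% |
| Favorable overrides, straight to 250 | 2.34% | 1.98% |

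The two-sided totals with the efficacy rule first and binding futility depend on the harm side. If futility applies in the benefit direction only, the harm tail is 0.04108/2 = 0.0205, and the totals are 4.92%, 4.76% and 4.62% down the first three rows. If futility applies symmetrically, they are 5.74%, 5.42% and 5.13%.

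**Overlap of interim zones.** With CP to 106, CP of 80% needs an interim p of 0.036 or less, which already crosses 0.04108. With CP to 124 it needs p of 0.0434 or less, which leaves a narrow band (0.0411 to 0.0434) that is Favorable without being a stop.

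**The case against.** The strongest objection is that 6.5% needs three conditions: the efficacy rule applied first, futility non-binding, and no increase. Protocol 12.5.3 words futility as an instruction and says 0.04108 was calculated for a design with both a futility and an efficacy stop. If futility binds in the benefit direction, the two-sided total is 4.6% to 4.9%, inside the stated 5%. A reading in which Favorable overrides the efficacy stop would fit the reported continuation, and leaves little or no inflation.

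What stands: the 6.5% is conditional, and the binding status of futility should be written down. What does not stand is relying on it. The plan never calls futility binding, requires all four sets to fall below the threshold, and has committees that only recommend. The two-sided total falls below 5% only because enforced futility removes harm-direction rejections at the final analysis. Success is defined in the benefit direction, where every efficacy-first reading computed exceeds 2.5%. No text gives Favorable precedence over the efficacy stop.

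Protocol 12.5.3 does mention 4.108% a second time, but for a sample size calculation. Used at both looks it would still give 5.8%.

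Two smaller points are fair. If the sponsor made futility binding on one analysis set, the final level holding benefit-direction error at 2.5% would be about 0.0326 at 86/106. And 77.8% power is a normal approximation; the t-test simulation gives 76.8%.

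**Conclusion.** The concern holds. The plan as written does not deliver its stated 5%. At 86 of 106 evaluable subjects, with futility non-binding and no sample size increase, overall two-sided error is about 6.5% and benefit-direction error 3.2% against 2.5%. At 124 analysed subjects the two-sided figure is 7.0%. These figures assume one analysis set decides and the efficacy rule is applied first. The absence of a reduced final level is certain from the sections available (SAP 10.1 to 10.3, on analysis sets, were not); the exact excess depends on how futility and the interim zones operate.

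Two related matters need reconciling and are not shown errors: 0.04108 does not follow from its named spending function at the stated timing, and the Favorable and efficacy-stop zones overlap when conditional power is taken to 106.

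**What to change.** Before unblinding, in SAP 11.5.1, protocol 12.9.1 and the SAP 9.2 gate:

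1. Replace 0.05 with the final two-sided level c that keeps overall two-sided alpha at 5% given the alpha available at the interim. Compute it from the evaluable subjects actually analysed at both looks, with futility non-binding. If 0.04108 stands, c is about 0.028 at 106 and about 0.022 at 124. Use c for the confidence interval tied to the success claim.
2. Reconcile 0.04108 with the stated Pocock-type spending before fixing c.
3. State which interim rule took precedence, which analysis set decided, and how conditional power was computed (106 or 124, assumed effect, critical value).
4. In the same success sentence, replace the word higher with a larger reduction (more negative change), because protocol 12.2.1 defines change as visit 4 minus baseline.
5. Restate power at 106 as about 78% with futility ignored (about 77% by t-test) and about 76% with it enforced.

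The cost is wording only, with no new data. The final threshold becomes stricter. By normal approximation at d = 0.55 and 106 subjects, power falls from 82.5% to 77.8% with futility ignored (4.7 points), or from 79.4% to 76.3% with it enforced (3.1 points). If 124 are analysed at 0.0219, power is about 82% with futility ignored.

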### 12.2. Study Endpoint Variables

#### 12.2.1. Primary endpoint variable

The primary endpoint is the change in HDRS17 total score from baseline to 8 weeks post treatment initiation, in each of the study groups. This variable will be calculated by subtracting the subject's baseline HDRS17 score from the score at visit 4.

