8.2 Secondary Efficacy Endpoints

Secondary efficacy endpoints include:

- **Proportion of responder subjects** - defined as the percent of subjects achieving at least 50% reduction from baseline in their HDRS-17 total score, 8 weeks post Relivion®DP treatment initiation.

- **Proportion of subjects achieving remission** - defined as the percent of subjects with HDRS-17 score≤7 at 8 weeks post Relivion®DP treatment initiation.
- **Change from baseline** to week-8 post Relivion®DP treatment initiation **in depressive symptoms** as measured by **MADRS** total score.

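### The direction clause in the primary success rule has the wrong sign for the change variable the protocol defines; one SAP sentence corrects it

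*SAP*

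**What the plan says.** Protocol 12.2.1 fixes the sign of the primary variable: "This variable will be calculated by subtracting the subject's baseline HDRS17 score from the score at visit 4". Protocol 12.4 reports the feasibility results on the same signed scale, with a "mean change of -5.95 points" at 3 weeks and then: "The 6 week results were a (baseline adjusted) mean change of -8.4 points".

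Lower HDRS-17 is better. SAP 8.2 defines response as the "percent of subjects achieving at least 50% reduction from baseline in their HDRS-17 total score", and remission as a score of 7 or less.

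SAP 11.5.1 models the change in HDRS-17 and takes LS means by group and visit. It then calls the study "successful if the p-value is <0.05 and the mean change HDRS-17 in the active group is higher than that of the sham group". Protocol 12.9.1 has the same condition: the mean change "in the active group is higher than that of the sham group".

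The hypotheses in Protocol 12.3 and SAP 2.2.2 are equality against inequality, and the test is two-sided at 5% (SAP 9.1). SAP 1 states that the SAP governs where it differs from the protocol.

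**The concern.** The hypotheses carry no direction and the p-value is two-sided, so a significant result alone does not say which arm did better. The step from primary testing to the secondary endpoints (Protocol 12.8.2, SAP 9.2) also depends on the p-value alone. The word *higher* in the success sentence is the one place where the plan turns a significant difference into a claim of benefit. On a variable where improvement is negative, *higher* means a smaller fall in the score.

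This is the formal criterion of a trial meant to support US and European marketing applications. A prespecified rule should give the right answer when followed as written. If it stays as it is, a positive trial would not meet its own stated criterion. The sponsor would then have to explain, with the results known, why the sentence was not applied literally.

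**Working it through.** **1. The plan's own figure.** Inputs from Protocol 12.4: difference 3.3, SD 6, two-sided alpha 0.05, power 80%.

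- Standardised effect: 3.3 / 6 = 0.55.
- Normal approximation: n = 2 × (1.960 + 0.842)² / 0.55² = 51.9, so 52 per group.
- Two-sample t-test: n = 52.87, so 53 per group, with power 80.1% at 53.

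The stated 53 per group (106 in total) reproduces. It does not depend on the wording of the success rule.

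**2. The rule on the protocol's illustration.** Protocol 12.4 gives a 6-week active mean change of -8.4. With an effect size of 0.5 and an SD of 6, it expects a sham reduction of 8.4 - 0.5 × 6 = 5.4 points. On the visit-minus-baseline scale, sham is -5.4.

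- Active minus sham = -8.4 - (-5.4) = -3.0, so active is better by 3.0 points.
- Is active higher than sham? -8.4 > -5.4 is false, so the literal rule is not met.
- With the arms exchanged (active -5.4, sham -8.4), the literal rule is met if p < 0.05, although active is worse by 3.0 points.

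**3. Probability of meeting each reading of the rule.** This uses 53 per group and the design assumptions.

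- SE = 6 × √(2/53) = 1.166.
- Noncentrality for a true benefit of 3.3 points: -3.3 / 1.166 = -2.83, with 104 degrees of freedom.

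| True active minus sham | Success means a more negative change on active | Success means a numerically higher change on active |
|---|---|---|
| -3.3 (benefit as assumed) | 80.1% | about 9.4 × 10⁻⁷ |
| +3.3 (equally large harm) | about 9.4 × 10⁻⁷ | 80.1% |

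The entries are from the noncentral t distribution; the second row follows from the first by symmetry. The normal approximation agrees: Φ(2.83 - 1.96) = 0.81 and Φ(-1.96 - 2.83) = 8.3 × 10⁻⁷. In substance the table shows the planned power and its opposite tail. It describes the literal sentence, not what an analyst would be expected to do.

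**4. Whether other text reverses the sign.** SAP 8.1 names the endpoint as a change from baseline without a subtraction order. The mock code in SAP 11.5.1 takes the change as a ready-made variable. Neither says that *higher* means a larger reduction or a larger absolute change. Elsewhere, where the SAP means a fall in the score, it says reduction, as in the response definition and the 7-point improvement endpoint (SAP 8.2 and 8.3). Protocol 12.2.1 therefore remains the only definition of the sign.

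**The case against.** The best reply is that nobody would misread this. The documents often describe HDRS-17 change as a positive amount: a 9-point improvement in the feasibility study (Protocol 7.6.2), a sham reduction of 5.4 points and an unsigned 3.3-point difference (Protocol 12.4). In that usage a higher mean change is a larger fall. The response and remission definitions settle which way benefit runs. SAP 11.5.1 also requires the adjusted mean for each arm and their difference with 95% confidence intervals, so the direction would be visible in the primary output. All of this stands. It limits the problem to wording, but does not make the sentence correct for the variable as defined.

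Three stronger readings are tempting, and the documents do not support them.

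- A reader might infer that the trial would reach the wrong conclusion. No estimate, test or sample size depends on the clause, and the intent is clear.
- A reader might infer that the interim rule for overwhelming results ("primary endpoint at the interim analysis is statistically significant at a 0.04108 level of significance, then stop the study for success") could have stopped the trial for success on a result favouring sham, because it states no direction. Protocol 12.5.3 bases the decisions on conditional power given the observed active-versus-sham effect, and a disappointing result goes most naturally to futility. In any case, SAP 2.2.1 reports that the interim analysis has been done, was favorable, and led to continuation at the planned size. An edit there would change nothing.
- A reader might infer that the 0.05 threshold in the same sentence needs changing too. Nothing in the direction problem bears on it.

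**Conclusion.** The point holds as an error in the written decision rule. On the variable defined in Protocol 12.2.1, the direction clause in SAP 11.5.1 and Protocol 12.9.1 points the wrong way, and no other text in the two documents corrects it. Taken literally, the rule would almost never be met by a device that works as assumed (about 9.4 × 10⁻⁷, against 80.1% with the direction corrected). It would be met 80.1% of the time by a device 3.3 points worse than sham. These figures rest on the plan's own difference, SD and 53 evaluable subjects per group, and on a two-sample t-test in place of the repeated measures model.

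The SAP's precedence clause does not resolve the conflict, because the SAP repeats the sentence and gives no sign convention of its own. The clause does mean that correcting the SAP is sufficient. The correction is needed because the sentence defines success in a pivotal trial, not because the analysis itself is faulty.

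**What to change.** Before unblinding, restate the success sentence in SAP 11.5.1 along these lines:

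*The study is successful if the two-sided p-value is <0.05 and the LS mean difference (active minus sham) in change from baseline HDRS-17 (visit 4 minus baseline) at week 8 is less than 0, i.e. a greater reduction with active.*

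This also puts the subtraction order into the SAP. Protocol 12.9.1 can be aligned at any later amendment. It does not justify an amendment by itself, since Protocol 14.8 requires investigator agreement, IRB/EC approval, site training and a new acknowledgement form. Leave Protocol 12.5.3 and the 0.05 threshold as they are for the purpose of this point.

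The cost is one sentence in a revised SAP, with no change to the model, programs, data collection or sample size. Timing matters: SAP 6 records that the treatment code had not been revealed when the SAP was finalised. A correction dated while that is still true cannot be questioned as driven by results.
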